**3. Study procedures**

**a) History and physical examination** a physical examination will not be performed, at the discretion of the investigator, when this has been performed in the past 3 months at Mayo Clinic. The MMSE test will be administered as described previously. The maximum score is 30 and a score of less than 21 is suggestive of dementia.

**b) Anorectal manometry** will only be performed when this has not been performed in the past 6 months at Mayo Clinic. After rectal cleansing with 1-2 magnesium citrate (Fleets®, C.B. Fleet, Lynchburg, VA) enemas, anorectal functions will be assessed using standard and established techniques in our laboratory. Anal pressures will be measured at rest, during squeeze, simulated evacuation, and a Valsalva maneuver by high-resolution manometry. Since clinical observations suggest that FI is also associated with a rectal evacuation disorder, rectal balloon expulsion will also be assessed.

**c) Flexible sigmoidoscopy** will be performed in the Clinical Research Unit after 1-2 Fleet's enemas. This is an optional procedure and will be performed in Phase 1 of the study after the rectal catheter and if an anorectal manometry is performed, after that procedure also. Using standard biopsy forceps, 8 mucosal biopsies will be obtained each from the sigmoid colon and the rectum. Eight biopsies will provide adequate tissue for microbial DNA extraction. If any abnormality is seen on sigmoidoscopy, additional biopsies will be obtained for histology. The colonic mucosal

[figure not shown]

Figure 2. Mega-Brush. A. Undeployed brush with blue sheath and the foam compressed inside a gelatin sheath. B. The foam is pushed out but not yet deployed C. Foam deployed. The foam shown in the figure has 20 pores per inch. We will be using one which is softer with 80 pores per inch.

microbiota will be compared to that evaluated with a rectal catheter.

d) Rectal catheter. This test will be done in all patients either just prior to anorectal manometry or during the initial visit in patients who do not have a manometry. The Mega Brush ® (provided by Capnistics LLC., Figure 2) is a mass cytology cell retriever system comprised of a foam sphere made of biocompatible material that is used to obtain specimens from the anorectum. It is FDA cleared (FDA K944614/A) for collection of mucosal specimen with an endoscope. . The foam is enclosed in a flexible outer tube and the tip covered by a gelatin cap. The diameter of the foam is 30 mm when fully deployed and the foam has 80 pores per sq. inch. We propose to introduce the catheter under direct vision during the rectal examination. Once the catheter is in the rectum, the capsule will be pushed out into the rectum and the cap allowed to dissolve over about 5 minutes. This will deploy the foam sphere. The foam sphere will be rotated 1-2 times in the rectum very gently with the help of the sheath. The catheter will then be slowly withdrawn. .

e) Calculating relative abundance of bacterial 16s rRNA to human DNA: Quantitative PCR will be used to assay the quantity of bacterial 16s rRNA in the stool sample. This will be normalized to a single copy human gene (e.g. TNF-alpha) as described in literature . The relative proportion of bacterial to human DNA will be calculated by first generating a standard curve by dilution series using purified plasmids containing a representative target (e.g. *E.coli* 16s rRNA or human TNF-alpha). Purified plasmids will be amplified in parallel with patient samples and a standard curve generated to assess number of copies of the target in each sample.

f) Fecal and colonic mucosal microbiome analysis: Microbial DNA will be extracted from stool and tissue samples using standardized methods [18]. Phylotype profiles of the microbiome from colesevelam and placebo treated FI populations will be generated using deep rDNA hypervariable tag sequencing of the hypervariable V3-V5 region of the SSU rRNA gene, which has been validated for use with human microbiomes and is one of the methods of choice for the HMP. With the longer reads from the MiSeq (250x250 paired end reads), our sequencing will include both the V3-V5 RGTs making for a more optimal phylogenetic analysis [19]. Phylotype profiles of the mucosa-associated microbiome will be generated using rDNA sequencing of the hypervariable V3-V5 region, which has been validated for standard use by the human microbiome project. The 500 base pair reads will ensure a better optimal phylogenetic identification. Barcoding samples prior to sequencing will yield approximately 20,000 reads/sample, ensuring detection of both dominant (core microbiome) and poorly represented taxa (variable microbiome). Identifying the existent taxa, diversity, and ecological relationships within each sample requires that we process large volumes of 16S DNA sequence data. In order to accomplish this task we will follow protocols that we have quantitatively shown to be optimal. Reads will be aligned using our own custom multiple alignment tool (TORNADO v2.0) that has been optimized the production of taxonomic calls and alignments for downstream analysis such as OTU clustering and phylogeny from paired end reads [20]. Sequences will be culled according to initial quality files using QIIME, pre clustered in order to reduce the number of unique reads due to sequencing errors using mother, and aligned using the new version of the TORNADO pipeline for paired end reads. TORNADO v2.0 will then be used to obtain the taxa calls that will be used in later correlation analysis. Second, quantitative PCR assays targeting functional genes mcrA and mrtA (methanogens) dsrA (sulfate-reducing bacteria) and hydA (hydrogen-producing bacteria) will be performed on both stool and mucosal samples following published protocols [21]. Similarly, different sulfate-reducing genera will be quantified with validated 16S primers. The abundance

of functional genes will be correlated to physiological parameters. Subsequent QPCR assays on microbial groups that are significantly distinct in sequencing analyses may also be performed.

(i) Nutritional Assessment: Habitual dietary intake will be assessed at baseline using an electronic graphical food frequency questionnaire (FFQ) (Viocare Technologies, Inc. [name]). This questionnaire is based on the Women's Health Initiative FFQ and has been adapted by VioCare in an electronic computer-administered format to evaluate dietary intake over a three month period. It employs the Minnesota NDS nutritional analysis database for nutrient analyses. The FFQ has been validated and compares well with nutrient intake validated against food records and four 24-hr dietary recalls (29, 30). (ii) Participants will keep food records of their actual dietary intake for 72 hours prior to collecting the stool specimens for microbiome analysis. The food records will be analyzed for energy, protein, fat, carbohydrate and fiber content by the CRTU nutrition staff using the ESHA Food Processor software (Version 10.15) developed by ESHA Research, Salem, Oregon 97309-1028.

g) Drug therapy Patients will be treated with colesevelam (1.875 gm) and clonidine (0.1 mg) twice daily or matching placebo for 4 weeks. Patients will need to discontinue any antidiarrheal medications from the start of Phase 1 through end of Phase 3. Loperamide tablets (2 mg) will be provided for rescue when patients experience intolerable diarrhea. Patients can take up to 3 unit doses in a 24 hour period, 5 unit doses in a 48 hour period or 10 unit doses in any 7-day period. They will be required to record their loperamide usage during the treatment phase.

h) Genome wide DNA analysis. We are currently exploring for SNPs associated with FI by genotyping 175 women with FI and 175 age- and gender-matched controls from Olmsted County (IRB 22-01), using a chip with > 500,000 SNPs spaced on average 1 every 5 kb in the genome. Towards our long-term objective of uncovering associations between SNPs and FI, we propose to extract DNA from 20 ml of blood, to be drawn from study participants. The tubes will be spun down in the Clinical Research and Trial Unit immediately and the plasma stored at minus 80 degrees celsius. The buffy coat will be stored at minus 80 degrees Celsius until DNA is extracted. DNA extraction will be conducted at the BAP Lab. Genome-wide analysis will be conducted using Illumina 610 QUAD microarray or comparable approaches. All patients who qualify for the study based on physician assessment in Phase 1 will undergo genotyping. Genotype-phenotype correlations will be examined using these patients and other patients in ongoing studies.

i) Analysis of Differential Gene Expression by RNA Seq analysis. In order to investigate if there is any relationship between the global gene expression in a patient and their response to treatment for FI, we will perform RNA Seq analysis with help of the Gene Expression Core Facility at Mayo Clinic Rochester. We will collect 7.5 ml of blood in PAX gene tubes at the time of the initial visit. RNA will be extracted from whole blood immediately and stored at minus 80 degrees celsius. Further processing of RNA will be done by the Gene Expression core facility at Mayo Clinic, Rochester.

**Summary of Blood Collections.** The total blood collected for this study is 27.5 ml.

Item	Test ID	Lab	Tube (amount required)
DNA for SNPs	31669	CRU Lab	Use buffy coat from EDTA tubes (one tube of 20 ml)

RNA extraction and processing	31669	BAP Lab	PAX gene tubes (7.5 ml)
-------------------------------	-------	---------	-------------------------

j) Symptom assessments.

The following instruments will be used to evaluate symptoms, co-morbid conditions, and impact on QOL.

- (i) Fecal Incontinence Severity Index (FISI) – which is a validated 4-item scale used to assess the frequency of 3 different types of FI. 
- (ii) Fecal Incontinence Quality of Life (FI-QOL) – is a 30-item validated questionnaire that assesses the effects of FI on QOL. 
- (iii) Hospital Anxiety and Depression (HAD) Scale 
- (iv) Health-status questionnaire (Radosevich DM, Wetzler H, Wilson SM. 1994. Health Status Questionnaire (HSQ) 2.0: Scoring Comparisons and Reference Data. Health Outcomes Institute, Bloomington, MN.) is a self-report inventory designed to measure a patient's overall health and functioning.
- (v) Fecal incontinence and Constipation Assessment (FICA) Scale – This validated instrument, developed in our program, has 4-items (frequency, type, amount of leakage, and presence of urgency) used to rate the severity of FI.  It is the only instrument that incorporates the amount of leakage, which is an important yardstick of the severity of FI.
- (vi) Satisfaction with treatment: In order to determine if patients were satisfied with the treatment received, we will use a previously validated visual analog score.

FICA score will be calculated from the bowel questionnaire. FISI, HAD, HSQ and Satisfaction with treatment score will be calculated from the General Questionnaire that will be administered pre and post-treatment (**Table 1**).

**Table 1. Symptom assessment tools and their administration during the study**

	Phase 1	Phase 2	Phase 3	Phase 4
Duration	Up to 1 week	2-4 weeks	4 weeks	4 weeks
Bowel questionnaire	X		X	X
Quality of life questionnaire	X		X	X
Hospital anxiety and depression questionnaire	X			X
Daily bowel diaries		X	X	X
Satisfaction with treatment			X	

4. Data and statistical analysis

i. Power Statement:

Based on the observed difference in the frequency of FI (i.e., mean number of FI episodes per subject per diem) between treatment and placebo groups in the clonidine study, we estimate that approximately 33 subjects in each treatment group (i.e. colesevelam and

clonidine vs placebo) will provide 80% power, using a two sided alpha level of 0.05, to detect at least a 50% difference in the frequency of FI between treatment groups.

ii. Data Analysis Plan:

a) Statistical analysis

An Excel (Microsoft, Redmond, WA) spreadsheet of treatment assignments (balanced on age and BMI) will be generated (by [name]) and sent to the research pharmacy. Study personnel will be blinded until the study is completed.

Bowel diaries will be analyzed as follows: Stool frequency, form, urgency and use of rescue medications will be averaged first for each day and then over 1-2 weeks (two weeks in Phase 1 and one week in Phase 3) in each subject.

We will compare response to treatment between colesevelam/clonidine and placebo between for the treatment period using the values during Phase 1 as covariates and separately, post-treatment. The analyses will use an  $\alpha$  value of 0.05 for each comparison. Treatment groups will be compared using analysis of covariance (ANCOVA) with the corresponding baseline (Phase 1) value as the covariate. Data will be analyzed per intent-to treat analysis using all subjects randomized. Missing values will be imputed as described previously and an adjustment in the ANCOVA error degrees of freedom will be made. Separate ANCOVA models will be used to evaluate whether treatment effects were influenced by the presence or absence of diarrhea at baseline. All tests will be two tailed.

Endpoints

The primary and secondary endpoints have been well described in our study of clonidine in FI and will be employed in this study as well

a) Primary endpoint:

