### 1. Phase 1 (Initial screening)

Patients who consent to participate in the study will visit with the investigator during which a physical examination may be performed. During this visit they will be asked to complete questionnaires designed

to determine whether or not they have FI, the type of FI, screen for anxiety or depression and assess quality of life at baseline. **Those who have diarrhea but not FI as assessed by the questionnaires (i.e. Bristol stool type 6 or 7, or >3 bowel movements/day on average) will be excluded from the study.** Eligible patients who give consent will undergo a urine pregnancy test, a 12 lead EKG, anorectal manometry (if not done at Mayo Clinic in the last 6 months), spot stool sample for microbiota analysis, blood draw for genotyping, assessment of the rectal mucosal microbiota with a rectal catheter, and an optional flexible sigmoidoscopy. Patients will be asked to record their dietary intake for 72 hours prior to collecting the stool sample.

Of these tests in phase 1, only the pregnancy test and EKG will determine whether patients proceed to phase 2. The remaining tests will be used to assess specific aims 2-5. Anorectal manometry will help clarify whether these patients have FI because of weakness of the anal sphincter or rectal hypersensitivity. The spot stool sample and rectal mucosal catheter will be used to assess the microbial diversity in FI. Among patients who have a flexible sigmoidoscopy, the mucosal microbiota will be compared on mucosal samples and a rectal catheter. In an attempt at (i) avoiding situations where we recognize subjects are not eligible to participate when they present at the screening visit and (ii) reduce the time taken for screening visits, we propose, when feasible, to ask participants to complete the questionnaires and a 2 week bowel diary before they come for their screening visit. Subjects will return these questionnaires to us by regular or electronic mail. If subjects are not subsequently consented/enrolled into the study, these items will be destroyed. [This bowel diary is identical to that approved for use later in the study.]

Figure 1. Study design

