### 2. Phase 2 (Completion of bowel diaries)

Patients, who have FI, as documented by the questionnaire during phase 1, are not pregnant, and do not have EKG exclusion criteria documented below will enter phase 2. During this phase, patients will fill out daily bowel diaries to ascertain if they have FI symptoms of sufficient severity. The duration of this phase is variable and ranges from 2-4 weeks as clarified below. Only those patients who meet *all* the following criteria at the earliest weekly review of the bowel diaries starting at week 2 i.e., (i) completion of at least 5 out of 7 days of the diary in the preceding week and 10 out of 14 in the preceding 2 weeks, (ii) experience at least 1 episode of FI per week averaged over 2 weeks, (iii) have a Bristol stool form score  $\geq 3$ , and (iii) an average stool frequency of  $\geq 1$ /day will enter the treatment phase. Patients who have not filled out the minimum number of days of bowel symptoms will be asked to fill out bowel diaries for an additional 2 weeks. Those who satisfy criteria at the end

of the two additional weeks will proceed to Phase 3. Otherwise their participation in the trial will be terminated and they will exit the study.

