## **C. Phase 3**

### Inclusion criteria:

- (i) Completion of at least 5 out of 7 days of the diary in the preceding week and 10 out of 14 in the preceding 2 weeks
- (ii) At least 1 episode of FI per week averaged over 2 weeks
- (iii) Average Bristol stool score of 3 or higher
- (iv) Average stool frequency of  $\geq 1$ /day

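### The diary baseline is taken from Phase 1, where no daily diary is scheduled; the mandatory pre-treatment diary is in Phase 2, and FI episodes are missing from the averaging rule

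*Combined protocol and SAP*

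**What the plan says.** Section C.4.ii (Statistical analysis) has one rule for reducing the diaries. Stool frequency, form, urgency and rescue use are "averaged first for each day and then over 1-2 weeks (two weeks in Phase 1 and one week in Phase 3) in each subject". Two further sentences set the covariate. Treatments are compared "for the treatment period using the values during Phase 1 as covariates and separately, post-treatment", using "analysis of covariance (ANCOVA) with the corresponding baseline (Phase 1) value as the covariate". The same section states: "Data will be analyzed per intent-to treat analysis using all subjects randomized".

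Table 1 gives Phase 1 a maximum of one week and marks daily diaries in Phases 2, 3 and 4 only. It marks the bowel, quality-of-life and anxiety/depression questionnaires in Phase 1 and not in Phase 2.

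Section C.1 places the pre-treatment diary in Phase 2: "The duration of this phase is variable and ranges from 2-4 weeks as clarified below". Patients with too few recorded days "will be asked to fill out bowel diaries for an additional 2 weeks". The Phase 3 inclusion criteria require at least 5 of 7 recorded diary days in the week before and "10 out of 14 in the preceding 2 weeks". The only diary mentioned under Phase 1 arises from a proposal, "when feasible, to ask participants to complete the questionnaires and a 2 week bowel diary before they come for their screening visit".

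The abstract sets the primary outcome, a reduction of at least 50% in FI episodes per day, at the completion of four weeks of treatment. The primary endpoint paragraph repeats the 50% threshold but names neither the baseline days nor the on-treatment days.

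**The concern.** The baseline does two jobs here. It is the reference for a 50% reduction, and so decides who is a responder, and it is the covariate in the ANCOVA. A rule that points to a phase without a scheduled diary leaves both undefined if it is read as written. Replacing the phase number throughout would create a new error, because the questionnaire endpoints do have their baseline in Phase 1.

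The rule also leaves out FI episodes. The primary variable therefore has no stated averaging rule, either before or during treatment, and the single Phase 3 week is not identified. Two analysts holding the same diaries could classify some patients differently.

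**Working it through.** **Baseline: the texts side by side.** The plan prints no figure that depends on the phase label, so this part is a comparison of text.

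| Question | Averaging rule and covariate sentences | Table 1 and Sections C.1, C.2 |
|---|---|---|
| Phase supplying the diary baseline | Phase 1 (named three times) | Phase 2 |
| Length available | Two weeks needed | Phase 1: at most one week. Phase 2: 2 to 4 weeks |
| Diary scheduled for all patients | Assumed | Phase 1: no. Phase 2: yes |
| Questionnaire baseline | Phase 1 | Phase 1 (agrees) |
| FI episodes covered | Not listed | Recorded in the diary |

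Two weeks cannot be drawn from a phase of at most one week. The pre-screening diary is requested only when feasible and is not in Table 1, so it cannot serve an analysis of everyone randomised. The Phase 2 diary can: entry to treatment requires at least 10 recorded days of the 14 before it. That qualifying fortnight is the natural baseline, but the analysis section does not say so.

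**On-treatment window: illustration only.** Every rate below is an assumption.

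- Baseline count B over two weeks is Poisson(2λ), conditional on B ≥ 2 (the entry rule of one episode per week over two weeks, complete diary).
- The on-treatment count Y over w weeks is Poisson(rλw), with r = 1 for no change and r = 0.5 for a true halving.
- Response means Y/w ≤ 0.5 × B/2, that is Y ≤ floor(0.25·B·w).
- P(response) = Σ P(B = b | B ≥ 2) × P(Y ≤ floor(0.25·b·w)), summed over b ≥ 2.

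For example, b = 2 allows Y = 0 on a one-week window, and Y ≤ 2 on a four-week window.

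| λ per week | No change: 1 week / 4 weeks | True halving: 1 week / 4 weeks |
|---|---|---|
| 1 | 45.7% / 40.9% | 68.0% / 80.0% |
| 2 | 32.0% / 16.9% | 60.8% / 62.2% |
| 3 | 24.2% / 9.6% | 58.0% / 56.8% |
| 4 | 19.3% / 6.1% | 56.5% / 55.2% |

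At 2, 3 and 4 episodes per week, individual status differs between the last week and the four-week mean in 25.5%, 20.9% and 17.4% of patients with an unchanged rate, and in 27.0%, 28.3% and 28.2% with a true halving.

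**Which Phase 2 days.** This arises only where Phase 2 runs four weeks. The simulation assumed 7 or 9 recorded days in the first two weeks, 14 in the last two, 2 to 4 episodes per week and a one-week outcome. Pooling all four weeks instead of using the last 14 days changed responder status in 4.9% to 9.9% of such patients. The documents do not say how many there would be.

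**The case against.** The strongest reply is that the documents largely resolve this themselves. Phase 2 holds the only mandatory pre-treatment diary, entry is judged on the fortnight just before treatment, and no analyst could extract two weeks from Phase 1. That stands as a reason to expect the right analysis in practice. It does not make the printed rule correct, and a simple relabelling would misplace the questionnaire baseline.

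A second reply is that the window is not really open. The abstract's time point and the single Phase 3 week together indicate the final week, while the four-week reading rests on a mention of the treatment period that may only name the phase. This mostly stands. A reader might infer two equally supported windows for the primary endpoint; the text does not bear that out. What remains is that no passage names the week and that the averaging rule does not list FI episodes.

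Third, the plan defers its endpoint definitions to the earlier clonidine study, which may state the window. That can be neither confirmed nor excluded here, so the gap is that the definition is not restated. The deferral is also imperfect: the sentence carries reference 34, which the reference list gives as a survey of community women, whereas the clonidine trial cited in the power statement is reference 17.

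Fourth, the disagreement figures can look worse than they are. Under a true halving every patient sits at the cutoff, and reclassification nearly cancels: 60.8% against 62.2% responders at 2 per week. Disagreement between windows is not bias between blinded arms. This stands.

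**Conclusion.** The baseline instruction is wrong as written and should be corrected. That finding rests on the text alone and is firm. The missing FI episodes and the unnamed Phase 3 week are omissions of detail, and the week is the lesser matter.

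A reader might infer that the trial lacks baseline data. It does not: the Phase 2 diary is a condition of randomisation, and diaries run daily through treatment. A reader might also infer that an arbitrary choice of Phase 2 weeks threatens the result. The first two weeks of an extended Phase 2 are an implausible baseline, because the extension applies only to patients whose early diary had too few recorded days. Pooling would affect only those patients, so its effect on the whole trial may be small.

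The size of any effect is illustrative. The figures assume Poisson counts, one common rate, no overdispersion and, for the window, complete diaries; the documents supply no FI rates. They show that chance response depends on the window when the true rate is unchanged. They do not settle which window is better: one week has more chance response, while a four-week mean dilutes an effect that builds slowly.

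**What to change.** 1. In the averaging rule, replace the two Phase 1 weeks with the qualifying last 14 Phase 2 diary days before randomisation, averaged per recorded day.
2. Add FI episodes to the variables that the rule covers.
3. In both covariate sentences, state that baseline is this Phase 2 value for diary endpoints and the Phase 1 value for questionnaire endpoints.
4. As a secondary clarification, before unblinding, name the Phase 3 week used for FI frequency, in the same words in the abstract, the endpoint paragraph and the analysis section. Week 4 is what the present text points to. Reporting the four-week mean as a supporting analysis would be good practice but is not needed to correct the error.

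The cost is a few sentences. No extra data, visits or patients are needed. The timing matters, because a window named after unblinding could not be shown to have been prespecified.
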